## 13.4.5 Descriptive Analyses

Descriptive statistics will be provided by treatment group for participant disposition, baseline and demographic characteristics, and use of concomitant medications. Continuous measures will be summarized using n, mean, standard deviation (SD), median, minimum, and maximum. Categorical variables will be summarized using counts and percentages.

#### 13.5 INTERIM ANALYSES

No formal interim analyses for stopping the trial early for futility or efficacy are planned.

#### 13.6 STATISTICAL HYPOTHESES

Statistical hypotheses are provided in Sections 13.4.2 and 13.4.4.

#### 13.7 SAMPLE SIZE CONSIDERATIONS

The underlying F-VASI35 response rate at Week 24 was assumed to be 5% for the placebo arm based on clinical trial results with ruxolitinib cream for vitiligo. For the AMG 714 arm, the minimal clinically meaningful response rate was assumed to be 45%. Under this scenario, a study of 57 individuals randomized 2:1 to AMG 714 and placebo, respectively, will provide 88% power using a 2-sided Fisher's Exact test at  $\alpha$ =0.05. If the placebo response rate is actually 7.5% (i.e. 50% higher than expected), power will still 81%. For the secondary PP analysis, if sample size drops to 48 (16% loss), then power is still 80%.

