# 13.4.2 Primary Analysis of Primary Endpoint

The primary endpoint is the proportion of participants achieving an F-VASI35 response at Week 24.

The primary analysis of the primary endpoint will be performed on the mITT sample and is designed to test the following hypotheses:

- Null hypothesis: The proportion achieving an F-VASI35 at Week 24 does not differ between the AMG 714 and placebo groups
- Alternate hypothesis: The proportion achieving an F-VASI35 at Week 24 differs between the AMG 714 and placebo groups.

The proportion of F-VASI35 responders will be estimated for each treatment group. Groups will be compared using two-sided Fisher's Exact test evaluated using a Type 1 error rate of  $\alpha$ =0.05.

**Missing Data.** For a participant who is missing the baseline F-VASI, the screening F-VASI will be used. Participants for whom the Week 24 F-VASI cannot be evaluated will be deemed non-responders.

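### The powers in Section 13.7 (88%, 81%, 80%) understate the two-sided Fisher's Exact test they are attributed to; exact values are 92.7%, 85.8% and 85.7%

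*Combined protocol and SAP*

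**What the plan says.** Section 13.7 assumes an F-VASI35 rate at Week 24 of 5% on placebo and 45% on AMG 714. On that basis, "a study of 57 individuals randomized 2:1 to AMG 714 and placebo, respectively, will provide 88% power using a 2-sided Fisher's Exact test" at a two-sided 0.05. Two further figures follow, both in per cent: "If the placebo response rate is actually 7.5% (i.e. 50% higher than expected), power will still 81" and, for the per-protocol analysis, "if sample size drops to 48 (16% loss), then power is still 80".

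The test is the one planned for the primary analysis. Section 13.4.2 states: "Groups will be compared using two-sided Fisher's Exact test evaluated using a Type 1 error rate" of 0.05.

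Three things are not stated: how power was calculated, which definition of the two-sided Fisher p-value applies, and how the 48 per-protocol participants divide between arms.

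**The concern.** A power attributed to a named exact test should be reproducible from that test. Here every input to the first two figures is given (sample size, allocation, both rates, alpha and test), so power can be calculated without approximation, and a standard calculation gives noticeably higher values. These are the only figures offered to justify N = 57.

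The unstated p-value convention is a related gap. With unequal arms, the two common definitions of a two-sided Fisher p-value can fall on opposite sides of 0.05 for the same table. That affects the power and, potentially, the primary result.

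**Working it through.** **Inputs.** From Section 13.7: N = 57 at 2:1, so 38 AMG 714 and 19 placebo; rates 45% v 5% and 45% v 7.5%; two-sided alpha 0.05; per-protocol N = 48. Assumption: 2:1 is kept at N = 48, giving 32:16.

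**Step 1: reproduce the stated figures.** The continuity-corrected arcsine approximation is

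power = Φ( 2·[asin√(p₁ − 1/(2n₁)) − asin√(p₂ + 1/(2n₂))] / √(1/n₁ + 1/n₂) − 1.960 )

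- 38:19, 45% v 5%: 2 × (0.7221 − 0.2799) / 0.2810 = 3.147; Φ(1.187) = 88.2%
- 38:19, 45% v 7.5%: 2 × (0.7221 − 0.3239) / 0.2810 = 2.834; Φ(0.874) = 80.9%
- 32:16, 45% v 5%: 2 × (0.7196 − 0.2891) / 0.3062 = 2.812; Φ(0.852) = 80.3%

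These round to 88%, 81% and 80%. Other methods fit less well: enumerating the continuity-corrected chi-square test gives 87.9%, 79.3% and 79.0%, and the pooled normal formula gives 93.5%, 87.7% and 87.9%.

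**Step 2: exact power of the named test.** For each pair of responder counts (x of n₁, y of n₂), compute the two-sided Fisher p-value and add the product of the two binomial probabilities wherever p ≤ 0.05. Two conventions were used: the usual one, which sums all tables no more probable than the one observed, and twice the one-sided p-value.

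For 38:19 and 45% v 5% with the usual p-value:

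| Placebo responders y | Probability of y | Smallest x that rejects | Probability of reaching it | Product |
|---|---|---|---|---|
| 0 | 0.3774 | 8 | 0.9994 | 0.3771 |
| 1 | 0.3774 | 11 | 0.9858 | 0.3720 |
| 2 | 0.1787 | 15 | 0.8011 | 0.1432 |
| 3 | 0.0533 | 17 | 0.5753 | 0.0307 |
| 4 | 0.0112 | 19 | 0.3227 | 0.0036 |

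The products sum to 0.9266. The remaining tables add about 0.0002, giving 0.9268. With doubling, the smallest rejecting x for y = 0 to 3 is 9, 12, 15 and 18, and power is 0.9114.

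**Step 3: all three scenarios.**

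| Scenario | Stated | Usual p | Gap (points) | Doubled p | Gap (points) |
|---|---|---|---|---|---|
| 38:19, 45% v 5% | 88% | 92.7% | 4.7 | 91.1% | 3.1 |
| 38:19, 45% v 7.5% | 81% | 85.8% | 4.8 | 83.2% | 2.2 |
| 32:16, 45% v 5% | 80% | 85.7% | 5.7 | 82.7% | 2.7 |

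**Step 4: dependence on the split at N = 48 (45% v 5%).**

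| Split | Usual p | Doubled p |
|---|---|---|
| 30:18 | 89.4% | 84.4% |
| 32:16 | 85.7% | 82.7% |
| 34:14 | 84.3% | 78.4% |

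**Step 5: effect of the p-value convention on the primary test.** Take 8/38 v 0/19 responders. The one-sided p-value is C(38,8)/C(57,8) = 0.0296, which doubles to 0.059. The usual convention adds the opposite-tail tables that are no more probable (0, 1 or 2 of the 8 responders on AMG 714, total 0.0127), giving 0.042. The same data are significant under one convention and not under the other.

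**The case against.** The strongest reply is that this is not an arithmetic slip. A recognised approximation reproduces all three figures to the rounded point, approximate power for an exact test is common practice, and Section 13.7 names the test without claiming enumeration. This explains the numbers but does not make them right: the section presents them as the power of the exact test and mentions no approximation. That the sponsor used this approximation is itself only an inference.

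The per-protocol comparison does depend on the split, and that limit stands. Exclusions can fall unevenly: with the doubled p-value, 33:15 gives about 81%, close to the stated 80%, and at 34:14 (78.4%) the stated figure is slightly too high. The first two comparisons need only the stated 2:1 allocation.

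It is also fair that the error is conservative, that Section 13.5 plans no formal interim stopping for futility or efficacy that could rest on these powers, and that nothing in the plan suggests doubling will be used. Leaving the convention unstated is therefore missing detail, not an error. These points limit the importance of the correction but do not remove the discrepancy.

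**Conclusion.** The concern holds. For the test named, the stated powers are too low by 4.7, 4.8 and 5.7 percentage points with the usual two-sided p-value, or by 3.1, 2.2 and 2.7 points with doubling. The first two results rest only on the plan's own inputs; the third also assumes 32:16. At 45% v 5%, the chance of missing the effect is 7.3% (100 − 92.7) or 8.9% (100 − 91.1), not 12%.

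The consequence is one of accurate reporting. N = 57 remains adequate under the plan's assumptions, and enrolment and analyses are unaffected. The correction should be made because the sole justification of the sample size cannot be reproduced from the test it cites, and because the p-value convention should be fixed before unblinding.

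**What to change.** Restate Section 13.7 along these lines:

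> Power was obtained by exact enumeration of the two-sided Fisher's Exact test at 0.05, with the p-value summing all tables no more probable than the one observed. At 38:19 it is 92.7% for 45% v 5% and 85.8% for 45% v 7.5%. For the per-protocol analysis at 32:16 it is 85.7% for 45% v 5%.

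If the doubled p-value will be programmed, use 91.1%, 83.2% and 82.7% instead. Name the same convention in Section 13.4.2.

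Optionally, show how missing data bear on the primary power, since Section 13.4.2 provides that "Participants for whom the Week 24 F-VASI cannot be evaluated will be deemed non-responders". The plan gives no missing rate, so this would be an illustration. It assumes equal missingness in both arms and that the stated rates apply to participants with data, so both rates are multiplied by one minus the missing fraction. If the stated rates already count missing as failure, this adjustment would double-count. With the usual p-value at 38:19, power is about 88% at 10% missing and 85% at 16% missing for 45% v 5%, and about 79% and 75% for 45% v 7.5%.

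The cost is one reworded paragraph in 13.7 and one clause in 13.4.2. N stays at 57.

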#### 14. IDENTIFICATION AND ACCESS TO SOURCE DATA

#### 14.1 SOURCE DATA

Source documents and source data are considered to be the original documentation where participant information, visits consultations, examinations and other information are recorded. Documentation of source data is necessary for the reconstruction, evaluation and validation of clinical findings, observations and other activities during a clinical trial.

#### 14.2 ACCESS TO SOURCE DATA

The site investigators and site staff will make all source data available to the Sponsor (DAIT/NIAID), ITN, and relevant health authorities. Authorized representatives as noted above are bound to maintain the strict confidentiality of medical and research information that may be linked to identified individuals.

# 15. QUALITY ASSURANCE AND QUALITY CONTROL

Each clinical site will perform internal quality management of study conduct, data collection, documentation and completion. An individualized quality management plan will be developed to describe a site's quality management. Quality control (QC) procedures will be implemented beginning with the data entry system and data QC checks that will be run on the

database will be generated. Any missing data or data anomalies will be communicated to the site(s) for clarification/resolution.

Following written SOPs, the monitors will verify that the clinical trial is conducted and data are generated, documented (recorded), and reported in compliance with the protocol, GCP, and the applicable regulatory requirements (e.g., Good Laboratory Practices (GLP), Good Manufacturing Practices (GMP)).

The investigational site will provide direct access to all trial related sites, source data/documents, and reports for the purpose of monitoring and auditing by the Sponsor, and inspection by local and regulatory authorities.

# 16. PROTOCOL DEVIATIONS

#### 16.1 PROTOCOL DEVIATION DEFINITIONS

**Protocol Deviation** – The investigators and site staff will conduct the study in accordance to the protocol; no deviations from the protocol are permitted. Any change, divergence, or departure from the study design or procedures constitutes a protocol deviation. As a result of any deviation, corrective actions will be developed by the site and implemented promptly.

Major Protocol Deviation (Protocol Violation) — A Protocol Violation is a deviation from the IRB approved protocol that may affect the participant's rights, safety, or well-being and/or the completeness, accuracy and reliability of the study data. In addition, protocol violations include willful or knowing breaches of human participant protection regulations, or policies, any action that is inconsistent with the NIH Human Research Protection Program's research, medical, and ethical principles, and a serious or continuing noncompliance with federal, state, local or institutional human subject protection regulations, policies, or procedures.

**Non-Major Protocol Deviation** – A non-major protocol deviation is any change, divergence, or departure from the study design or procedures of a research protocol that does not have a major impact on the participant's rights, safety or well-being, or the completeness, accuracy and reliability of the study data.

#### 16.2 REPORTING AND MANAGING PROTOCOL DEVIATIONS

The study site principal investigator has the responsibility to identify, document and report protocol deviations as directed by the study Sponsor. However, protocol deviations may also be identified during site monitoring visits or during other forms of study conduct review.

# 17. ETHICAL CONSIDERATIONS AND COMPLIANCE WITH GOOD CLINICAL PRACTICE

#### 17.1 STATEMENT OF COMPLIANCE

This clinical study will be conducted using good clinical practice (GCP), as delineated in Guidance for Industry: E6(R2) Good Clinical Practice: Integrated Addendum to ICH E6(R1), and according to the criteria specified in this study protocol. Before study initiation, the protocol and the informed consent documents will be reviewed and approved by the IRB.

Any amendments to the protocol or to the consent materials will also be approved by the IRB before they are implemented.

#### 17.2 INFORMED CONSENT PROCESS

The consent process will provide information about the study to a prospective participant and will allow adequate time for review and discussion prior to his/her decision. The principal investigator or licensed physician designee listed on the FDA 1572 will review the consent and answer questions. The prospective participant will be told that being in the trial is voluntary and that he or she may withdraw from the study at any time, for any reason. All participants will read, sign, and date a consent form before undergoing any study procedures. Consent materials will be presented in participants' primary language. A copy of the signed consent form will be given to the participant.

The consent process will be ongoing. The consent form will be revised when important new safety information is available, the protocol is amended, and/or new information becomes available that may affect participation in the study.

# 17.3 PRIVACY AND CONFIDENTIALITY

A participant's privacy and confidentiality will be respected throughout the study. Each participant will be assigned a unique identification number and these numbers rather than names will be used to collect, store, and report participant information. Site personnel will not transmit documents containing personal health identifiers (PHI) to the study Sponsor or their representatives.

## 18. Publication Policy

The ITN policy on publication of study results will apply to this study. Authorized participants may find details regarding the policy statement on the ITN internet website at http://www.immunetolerance.org.

#### **APPENDIX 1. SCHEDULE OF EVENTS**

Phase of Trial	SCRN			Do	sing				Post-t	reatme	ent (FU	) 	WD 	UN 
Week		0	2	4	6	8	10	12	18	24	36	48	WD	U
Visit 	V-1	V0	V1	V2	V3	V4	V5	V6	V7 	V8	V9	V10	WD	U
	G	ENE	RAL	ASSE	SSMI	ENTS								
Informed consent	X													
Eligibility criteria	X													
Randomization 		X												
Medical history & demographics	X													
Vitiligo history	X													
Concomitant medications	X	X	X	X	X	X	X	X	X	X	X	X	X	X
Comprehensive physical examination	X							X		X		X	X	
Limited physical examination		X	X	X	X	X	X				X			X
Vital signs	X	X	X	X	X	X	X	X		X	X	X	Х	X
Adverse events	X	X	X	X	X	X	X	X	X	X	X	X	Х	X
Treatment Assignment Survey								X					Х	
	STUE	Y DI	RUGA	ADMI	NIST	RAT	ION							
Study drug (AMG 714 or placebo)		X	X	X	X	X	X							
		PI	ЮТО	THE	RAPY	Z .	 	 	 		 		 	
nbUVB phototherapy 										X	X	X		

Protocol ITN086AI: REVEAL Evaluation of AMG 714 for Vitiligo

<sup>1 After Week 12, remote follow-up contact will occur at least once between each visit to facilitate participant retention, and to discuss phototherapy in participants receiving this treatment after Week 24.

<sup>2 See Sections 11.2 and 11.4 for additional information related to the early study withdrawal visit.

<sup>3 Some assessments for an unscheduled visit may be omitted at the discretion of the principal investigator if not indicated.

<sup>4 Remote visit allowable if indicated at V1, V2, V4, and V5.

<sup>5 V7 will be conducted as a telephone visit (Section 8.4).

<sup>6 Randomization must occur at least one day prior to V0.

<sup>7 Participants will undergo narrow band ultraviolet B (nbUVB) phototherapy if T-VASI does not improve by  $\geq$  25% at Week 24 compared to Week 0.

Phase of Trial	SCRN	Dosing Post-treatment (FU) 				) 	WD 	UN 						
Week		0	2	4	6	8	10	12	18	24	36	48	WD	U
Visit 	V-1	V0	V1	V2	V3	V4	V5	V6	V7 	V8	V9	V10	WD	U
	CLINICA	L LA	BOR	ATOR	YAS	SESS	MEN	TS						
Hematology (CBC w/diff and plt)	X	X			X			X		X	X	X	X	X
Chemistry (Cr, T bili, AST, ALT, ALP, albumin)	Х	x			X			X		X	X	X	X	x
TSH	X													
HIV	X													
Hepatitis B (core Ab & surface Ag)	X													
Hepatitis C (RNA or antibody)	X													
Quantiferon-TB Gold/Quantiferon-TB Gold Plus 	X													
Serum pregnancy	X													
STAT urine pregnancy		X	X	X	X	X	X	X		X	X	X	X	
	V	ITIL	IGO A	ASSE	SSMI	ENTS					I	l	l	
F-VASI	X	X			X			X		X	X	X	X	X
T-VASI	X	X			X			X		X	X	X	X	X
VES		X			X			X		X	X	X	X	
VitiQoL		X			X			X		X	X	X	X	
VNS					X			X		X	X	X	X	
sIGA		X						X		X	X	X	X	
Digital skin photography		X						X		X		X	X	

<sup>8 PPD skin test may be substituted.

Phase of Trial	SCRN			Dos	sing				Post-t	reatme	ent (FU	) 	WD 	UN 
Week		0	2	4	6	8	10	12	18	24	36	48	WD	U
Visit 	V-1	V0	V1	V2	V3	V4	V5	V6	V7 	V8	V9	V10	WD	U
	MECHANISTIC ASSESSMENTS													
Skin biopsy – lesional 		X						X		X		X	X	
Skin biopsy – non-lesional		X						X						
PBMCs		X			X			X		X	X	X	X	
Serum		X			X			X		X	X	X	X	
Whole blood RNA		X			X			X		X	X	X	X	
Whole blood DNA		X			X			X		X	X	X	X	

Protocol ITN086AI: REVEAL

Version 4.0

November 3, 2023

 $^{9}$  If the lesion has resolved, the punch biopsy will be taken from the previously lesional area.

#### **APPENDIX 2. VASI**

#### Vitiligo Area Scoring Index (VASI)

The vitiligo area scoring index (VASI) is a quantitative clinical tool to assess the area affected by vitiligo. The body is divided into 6 separate regions:

- Head and neck (includes face)
- Upper extremities (excluding hands). The axillae are considered part of the upper extremities.
- Hands
- Torso (excluding axillae). The genitalia are not included in the VASI assessment.
- Lower extremities (excluding feet). The buttocks and inguinal area are considered part of the lower extremities.
- Feet

For each body region, the VASI is determined by the product of the area of vitiligo in hand units and the extent of depigmented skin within each hand unit-measured patch (estimated to the nearest of the following percentages: 0%, 10%, 25%, 50%, 75%, 90% or 100%).

#### **Body Surface Area (BSA)**

The percentage of the body surface area (BSA) affected with vitiligo can be estimated by the hand unit or thumb unit to the tenth decimal (0.1%). A hand unit encompasses the palm plus five digits, with fingers and thumb apposed. The hand unit is approximately 1% of the total BSA and the thumb is approximately 0.1% of the total BSA. The hand unit is based on each individual participant's own hand size.

#### Calculation of the T-VASI

The total body VASI is then calculated using a formula that includes a contribution from all body sites, with a possible range of 0-100%.

$$VASI = \sum$$
 [Hand Units] x [Residual Depigmentation]

All body sites

The evaluable area for the T-VASI assessment is all of the following:

- 1. The total body including the face and neck, and excluding the genitalia.
- 2. Vitiligo lesions on fingers including and distal to the proximal interphalangeal joints, toes, palms, and soles will not be included in the T-VASI assessment.

#### Calculation of the F-VASI

The F-VASI will be calculated separately. The F-VASI will be calculated in the same fashion as the T-VASI, except that the evaluable area is limited to the face only (see above). The %BSA will be measured to the tenth decimal (0.1%). The evaluable area is all of the following:

1. From the top of the forehead at the hairline down to the jawline, and from the right to the left tragus anteriorly, excluding mucosal lips. For participants who have a receding hairline, the original hairline should be used as the border for the face.

# Illustrations of Percent Depigmentation for the Vitiligo Area Scoring Index for the F-VASI and the T-VASI

1.0	Completely depigmented skin
(100%)	
0.90	Specks of pigmented skin present
(90%)	
0.75	Depigmented area exceeds the
(75%)	pigmented area
0.50	Pigmented and depigmented areas
(50%)	are equal
0.25	Pigmented area exceeds
(25%)	depigmented area
0.10	Only specks of depigmented skin
(10%)	present
0.00	No depigmented skin present
(0%)	

# **VASI Calculation Methods**

# F-VASI

[figure not shown]
Maximum BSA for	%BSA	Residual	F-VASI Score
Face	(Hand/Thumb Units) rounded to the nearest tenth	Depigmentation % (0.0 – 1.0)	(Hand/Thumb Units) x Residual Depigmentation
3.5%			

# T-VASI

[figure not shown]
Total Body	Maximum BSA per Body Area	%BSA (Hand/Thumb Units) rounded to the nearest tenth	Residual Depigmentation % (0.0 – 1.0)	% Area Involved (Hand/Thumb Units) x Residual Depigmentation
Head and neck (includes face)	9%			
Upper extremities, including axillae (excluding hands)	14%			
Hands	4%			
Torso (excluding axillae and genitalia)	32%			
Lower extremities, including buttocks and inguinal area (excluding feet)	36%			
Feet	4%			
$T-VASI = \sum [Han]$	d/Thumb Units]  All body regions	x [Residual Depigment	ration]	

# **APPENDIX 3. VES**

The Vitiligo Extent Score (VES) is determined *during* the patient encounter using the calculator at www.vitiligo-calculator.com as follows: For each area, select 1 picture which best represents the extent of the vitiligo lesions. There are additional options for quantifying the extent, e.g. if the extent is half (½) or a quarter (¼) of the involved area in the picture or slightly less (-) or slightly more (+) than the involved area in the picture. The ">75%" option can be selected if the involved area is more than shown in the last picture, but less than 100% (i.e. complete depigmentation). The calculator will use the selected images to calculate the percentage of the body surface area (BSA) involved or grade of extent per region (Grade 0 to 6).

© 2015. Nanja van Geel, Reinhart Speeckaert. All rights reserved.

© 2015. Nanja van Geel, Reinhart Speeckaert. All rights reserved.

# APPENDIX 4. VITIQOL

Vitiligo-specific Health-related Quality-of-life Instrument (VitiQoL) is a validated instrument that asks participants to rate various aspects of their vitiligo during the past month. Assessment will be conducted at the baseline visit, as well as visits during and after treatment per Appendix 1. The response to each question will be scored on a 0 (not at all) to 6 (all of the time) scale.

Du	ring the past month,	Not at all					All	of e time
		4			•			4
1.	Have you been bothered by the appearance of your skin condition?		ο,	□₂		□₄	□,	۵,
2.	Have you felt frustrated about your skin condition?	□₀	$\Box$ ,			□₄	□₅	□₊
3.	Has your skin condition made it hard to show affection?	$\Box$	$\Box$	Π,	□,	$\Box_4$	□,	$\Box_{\iota}$
4.	Has your skin condition affected your daily activities?	□.			D 3	□₄	□₅	□,
5.	When you were talking to someone, have you worried about what they may be thinking of you?	.	- 1	□₂	D 3	□ ₄		□,
6.	Have you been afraid that people will find fault with you?	□∘			D 3	□₄	□₅	□,
7.	Have you felt embarrassed or self-conscious because of your skin?	.	-	□₂	□,	ا	- ;	п ,
8.	Has your skin condition influenced the clothes you wear?	$\Box$			Π,	۵	□s	□₊
9.	Has your skin condition affected your social or leisure activities?	□.	$\Box$ ,		□,	□₄	□,	□,
10.	Has your skin condition affected your emotional well-being?	□.	$\Box$ ,		□,		□,	□,
11.	Has your skin condition affected your overall physical health?	□₀	$\square_1$		□,	□₄	□,	□,
12.	Has your skin condition affected your grooming practices (i.e. hairstyle, use of cosmetics)?	.		□ ₂	D 3	۵,	- .	۵,
13.	Has your skin condition affected your sun protection efforts during recreation (i.e. limiting exposure time during peak sun hours, seeking shade, wearing hat, long sleeves or pants)?	.	- ,	D 2	σ,	□₄	ο,	□,
14.	Has your skin condition affected your chances for making new friends?	.	ο,	D 2	□,	□₄	□,	□ .
15.	Have you worried about progression or spread of disease to new areas of the body?	□.	ο,	۵	ο,	□₄	۵	□,
	se check how severe you currently feel your condition is:	No ski involve					severe	Most case
16.	Severity of skin condition.		П.	П.	П	Π.	Π.	П.

